O09.2	14-19	Completed weeks
O09.3	20-25	Completed weeks
O09.4	26-33	Completed weeks
O09.5	34-36	Completed weeks
O09.9	Unspecified duration of pregnancy	

The yellow highlights are periods outside of the inclusion criteria.

Codes O09 should also have the following codes assigned for additional diagnoses:

Abortion	O00-007	Pregnancy with abortive outcome
Threatened abortion	O20.0	
Fetal death in utero	O36.4	
Premature rupture of membranes	O42	Before 37 completed weeks of gestation
Threatened premature labour	O47.0	False labour Before 37 completed weeks of gestation
Early onset of labour	O60	Early Preterm labour

Example

Patient admitted at 28 weeks gestation with a diagnosis of fetal death in utero (FDIU)

Medical and surgical induction of labour

O36.4	Maternal care for intrauterine death
O60.1	Preterm labour with preterm delivery
O09.4	Duration of pregnancy 26-33 weeks
Z37.1	Single stillbirth

1527- O48 will indicate prolonged pregnancy post dates and post term.

Some women deliver outside the hospital setting and this is estimated by the MoH at around 2%; however, information about these births is available via the National Maternity

Collection. All births, regardless of delivery setting, are assigned a unique National Health Index number. This allows capture of all post-birth hospital and/or notification events for all infants.

Inclusion criteria

Women

NZ women who are pregnant during the study period

Infants

Infants of the women who were pregnant during the study period

Study Two: Prospective intensive monitoring study of safety in pregnant women administered Tdap vaccination

This is a prospective observational study. It will describe any adverse events in pregnant mothers who received Tdap occurring within one month following immunisation. The data for this part of the study will be collected using the same methodology as that currently being used in Canterbury (i.e., Study Three currently in progress) and will therefore be directly comparable and also joint analysis will be possible for the maternal outcomes.

NOTE: We will not have any cases of spontaneous abortion in Studies Two and Three as the lower gestation eligible for vaccination and therefore inclusion in the study is 28 weeks.

Study population

All women vaccinated during pregnancy at any General Practice in NZ with Tdap vaccine will form the Study Two population.

Study participants

Study Two will include women 28–38 weeks pregnant.

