Rates and patterns of adverse events in women who were administered Tdap during pregnancy

Multiple pregnancies

While the number of visits during pregnancy could have an impact on the pregnancy outcome within the study population in Study Two and Three (but not in Study One). The frequency of prenatal care is a potential confounder as it may be associated both with women receiving Tdap or not, and with birth outcomes. There is no way to capture the number of prenatal visits women have from nationally available data. However, the National Maternity Collection does “contain data on primary maternity services provided under Section 88 of the NZ Public Health and Disability Act 2000. This information is sourced from lead maternity carer claims for payment.” This information might be useable as a proxy to indicate frequency of prenatal care.

Study Three: Intensive monitoring study of pregnant women administered Tdap during pregnancy and their infants

Study Three involves extending and supporting the intensive monitoring study currently being conducted in the Canterbury DHB by [name] (Principal Investigator). Briefly this study runs as per Study Two except the women and their infants are followed up intensively for a period of one year after the birth of the infant. The data collected for the period of one month post vaccination in Study Three will be able to be pooled for the overlapping subset of participants also in Study Two.

Study Three includes women receiving the vaccine under the DHB programme at 30–36 weeks in the Canterbury region.

Figure 1. Study population and outcomes

[figure not shown]
[figure not shown]

Figure 2. Monitoring of pregnant women receiving pertussis during pregnancy

Canterbury DHB continues intensive follow up for birth outcomes and infant outcomes for one year for a sample of 300 women and their infants. Infant follow up at three to seven months and 12 months of age in this DHB as per Canterbury protocol (Study Three) (Appendix 8).

Study procedures

Study One (utilising whole population data-linking)

Data sets for hospitalisations, pertussis notifications, infant vaccination and maternal Tdap vaccination will be obtained for the period 1 January 2009 to year ending 2013 from the following national databases:

- National Minimum Dataset for hospitalisation data
- The National Immunisation Register for infant immunisation data
- Notification data from the ESR
- Pregnancy Immunisation records from the HealthPAC claims database

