- Estimated minimum and maximum number of women for follow up of pertussis vaccine 1,527–20,358

Sample size and power

As this is an observational study we plan to describe the confidence intervals for the proportions of AEs. With a sample of 300 vaccinated participants, if event occurs in 10% of the group the 95% CI would be 7–14%; if 5%, 2.8–8.1%; if 1%, 0.2–2.9%. Additional power will be achieved by combining the data from the Canterbury study (Study Three), which aims to include 300 women vaccinated with Tdap.

Statistical Analyses

The pregnancy safety data will be descriptive in nature, including percentages and 95% confidence intervals. The rates of AEs and SAEs following pertussis vaccine will be discussed in context with the rates previously described for pertussis. The expected background rates of MAEs and SAEs for Tdap given during pregnancy are unknown, but as a guide the rates of MAEs for pregnant women receiving influenza vaccine previously reported ranged from 1.1 to 3.8% while the rate of SAEs ranged from 0.4 to 1.5%.

Women who have complicated pregnancies will be excluded from the final analyses and described separately.

The temporal relationship between onset of events and vaccination will be presented including distribution where appropriate.

Serious adverse events will be reported as detailed clinical cases. Other events will be groups according to Brighton Collaboration Definitions.

Study Three (N=~300)

From the protocol for Canterbury DHB (Appendix 8): Principal Investigator, [name].

As this study is an observational study, the pregnancy outcomes and safety data will be descriptive in nature. The rates of AEs and SAEs will be compared to published background rates for the general population. The expected rates of MAEs and SAEs for Tdap given during pregnancy is unknown, but as a guide the rates of MAEs for pregnant women receiving influenza vaccine in this paper ranged from 1.1 to 3.8% while the rate of SAEs ranged from 0.4 to 1.5%. Where the known background incidence of 0.01 for a particular adverse event, a sample size of 300 achieves 80% power to detect an additional incidence rate of 0.0175 when the significance level is 0.05.

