It is anticipated that the difference in AEs between subgroups in the trial will be small. As this is an observational study we therefore plan to describe the confidence intervals for the proportions of AEs within each group. A sample size of 300 produces a two-sided 95% confidence interval with a width equal to 0.081 when the sample proportion is 0.150.

Women who have multiple pregnancies and/or complicated pregnancies will be excluded from the final analyses and described separately.

Total expected participants

	Study population	Sample size	
--	------------------	-------------	--

Study One	325,000		Total pertussis-vaccinated maternal population
Study Two	1,527–20,358	300	~300 pertussis vaccinees
Study Three	6,000	300	300 pertussis vaccinees

Vaccines

Pertussis vaccine

The pertussis vaccine funded for pregnant women is Boostrix[®]. There are other licensed vaccines but no other pertussis vaccines currently funded for pregnant women in NZ.

Specific vaccine supply requirement

N/A. This is an observational study. There are no vaccine requirements for this study.

Adverse experience reporting

Adverse Event data are being accessed/collected during this project in Study Two and Three.

The Investigator will report SAEs (either initial or follow-up reports) to:

The NZ Centre for Adverse Reaction Monitoring (CARM) at the University of Otago according to local requirements. (See Appendix 9, contract Exhibit D, CARM Reporting Form)

The Ethics Committee according to requirements

The Marketing Authorisation Holder within 24 hours according to contracted safety reporting requirements defined in the study contract. Case reporting will include the relevant variables in the GSK “with intensity GCSP reporting form”. (See Appendix 10)

Administration during pregnancy is relevant in the age group, so pregnancy reporting is expected to be relevant. All participants will be pregnant.

There will be no causality assessments conducted during this study as this is observational and there is no intervention.

Any adverse events that are reported to the NZ Centre for Adverse Reaction Monitoring (CARM) undergo causality assessment. This data is provided to the WHO and the MoH.

CARM is the official regulatory body in charge of receiving all adverse event reports in NZ. CARM collaborates with and pools anonymised data, together with other national monitoring centres, into the database of the World Health Organization's International Drug Monitoring Programme.

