Serious adverse events—Study One

There will be no individual case adverse event reporting for Study One, which is a retrospective study using data linkage.

Serious adverse events—Study Two

This study is following women for four weeks following vaccination. Should there be any cases of stillbirth, fetal death, spontaneous abortion, elective abortion or other significant pregnancy outcomes during the period of active data collection, that we become aware of, these will be reported within 24 hours.

Reporting will occur on pregnancy outcomes, fetal outcomes and neonatal status at the end of the study for the Study One participants.

There will be no causality assessment performed as the study staff will not be able to do this based on telephone interviews. However causality process is undertaken via the established NZ CARM process.

The investigators and study team will be clearly informed and reminded of the importance of this timely reporting of any SAE to CARM.

Serious adverse events—Study Three

This study is following women for 12 months following vaccination. Should there be any cases of stillbirth, fetal death, spontaneous abortion, elective abortion or other pregnancy outcomes during the period of active data collection these will be reported within 24 hours of notification.

There will be no causality assessment performed as the study nurses will not be able to do this based on telephone interviews.

The investigators and study nurses will be clearly informed and reminded of the importance of this timely reporting of any SAE to CARM.

Data sharing with OCEANS database

We intend to enable data sharing for Study Two and Three with the OCEANS database. We await information from GSK on the database requirements. Data sharing of de-identified information will enable rapid transfer of information on both serious and **non-serious adverse events**. The data sharing will be covered in the Ethical approval and in the patient informed consent.

The data to GSK will be provided in MS Excel format. All variables collected in Study 2 and 3 will be provided in this file.

Other adverse event reporting:

Adverse events not meeting criteria for an SAE that are subject to clinician verification/review will be reported to CARM according to local requirements at the discretion of the clinician/investigator.

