f) Medical or scientific judgment should be exercised in deciding whether reporting is appropriate in other situations, such as important medical events that may not be immediately life-threatening or result in death or hospitalisation but may jeopardise the subject or may require medical or surgical intervention to prevent one of the other outcomes listed in the above definition. These should also be considered serious. Examples of such events are invasive or malignant cancers, intensive treatment in an emergency room or at home for allergic bronchospasm, blood dyscrasias or convulsions that do not result in hospitalisation, or development of drug dependency or drug abuse.

AE definitions

An AE is any untoward medical occurrence in a patient or clinical investigation subject or consumer, temporally associated with the use of a product, whether or not considered related to the product.

Examples of an AE include:

Exacerbation of a chronic or intermittent pre-existing condition including either an increase in frequency and/or intensity of the condition

New conditions detected or diagnosed after investigational product administration even though it may have been present prior to the start of the study

Signs, symptoms, or the clinical sequelae of a suspected interaction

Signs, symptoms, or the clinical sequelae of a suspected overdose

Examples of an AE do not include a/an:

Medical or surgical procedure (e.g., endoscopy, appendectomy); the condition that leads to the procedure is an AE

Situations where an untoward medical occurrence did not occur (social and/or convenience admission to a hospital)

Anticipated day-to-day fluctuations of pre-existing disease(s) or condition(s) present or detected at the start of the study that do not worsen

The disease/disorder being studied, or expected progression, signs, or symptoms of the disease/disorder being studied, unless more severe than expected for the subject's condition

All as per Brighton Collaboration where these definitions are available.

Definitions for local reactions and fever	
Local Reactions	Systemic Events

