Appendix 6: Study Two Phone Survey 1 (48hrs–7days post vaccine)

[name]
 Department of General Practice & Primary Health
 SCHOOL OF POPULATION HEALTH
 The University of Auckland
 [name]
 Auckland, 1142
 [contact]

PIPS Study Patient Participant Phone Interview 1 (48 hours–7days post vaccine)

The following questions ask about your memory of events for the period immediately (within 48 hours) following when you received the dose of Tdap vaccine (whooping cough vaccine).

Since having the vaccine, have you experienced any of the following at the place on your arm where you had the injection?

[Tease out potential symptoms and events related to vaccination eg, distinguish between what may be related to pre/post-pregnancy, “is this more than usual?”]

If you have had any redness or swelling, use the clear plastic measure the practice nurse gave you.

Use the smallest circle you can use to cover all of the redness or swelling, and this will give you the measurement of the reaction. If the reaction is bigger than the biggest circle, use the ruler down the side.

Event	Description/Question	Grade/Response	
1a. Redness	Has there been any redness where the injection was given?		
	No redness — go to next question	0	
	Yes, take measurement (measure tool used  OR estimate )	1	
 
 >0.0 – <1.0cm	2	
 
 =>1.0 – <2.5cm	3	
 
 =>2.5 – <5.0cm	4	
 
 =>5.0 – <10.0cm	5	
 
 =>10.0 – <15.0cm	6	
 
 =>15.0 – <20.0cm	7	
 
 =>20.0 – <30.0cm	8	
 
 =>30.0cm	9	
 
  1b. Induration	Is/was there a hard, woody lump with defined edges, where the injection was given?	
	No induration — go to next question	0	
	Yes, take measurement (measure tool used  OR estimate )	1	
  
 
 
 
© Immunisation Advisory Centre, The University of Auckland_V2_29/10/2013
		

	>0.0 – <1.0cm	2							
	=>1.0 – <2.5cm	3							
	=>2.5 – <5.0cm	4							
	=>5.0 – <10.0cm	5							
	=>10.0 – <15.0cm	6							
	=>15.0 – <20.0cm	7							
	=>20.0 – <30.0cm	8							
	=>30.0cm	9							

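### The Study Two first phone survey asks interviewers to separate vaccine-related from pregnancy-related symptoms, against the protocol's own adverse-event definition and with no field to record the judgement

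*Protocol*

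**What the plan says.** Appendix 6 opens with a question about events at the injection site. Below it stands a bracketed note to the interviewer: "Tease out potential symptoms and events related to vaccination eg, distinguish between what may be related to pre/post-pregnancy". The note ends with a sample prompt, asking the woman whether what she describes exceeds what is usual for her. Items on redness, induration, swelling, pain and fever follow, and then a general question on other symptoms that lists nausea, vomiting or diarrhoea, headache, fatigue, muscle or joint pain, shivering and a free-text item.

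Three other parts of the protocol bear on this:

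- **AE definitions.** An AE is an untoward occurrence "temporally associated with the use of a product, whether or not considered related to the product". Worsening of a pre-existing condition counts. Expected fluctuation without worsening does not.
- **Adverse experience reporting.** "There will be no causality assessments conducted during this study as this is observational and there is no intervention". For Study Two the reason given is: "There will be no causality assessment performed as the study staff will not be able to do this based on telephone interviews". Causality is left to CARM, the national monitoring centre.
- **Endpoints and pooling.** The Study Two endpoint is "Rates and patterns of adverse events in women who were administered Tdap during pregnancy". The data are to be "collected using the same methodology as that currently being used in Canterbury" and "will therefore be directly comparable and also joint analysis will be possible for the maternal outcomes".

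**The concern.** The endpoint is a set of rates of events counted whatever their cause. The note asks the person collecting those events to consider cause while eliciting them, over the medium that the protocol says cannot support such a judgement. Symptoms of late pregnancy overlap with the general symptoms that follow vaccination, so any sorting would act most on nausea, headache, fatigue and aches.

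The form keeps no trace of the sorting. A symptom set aside as due to pregnancy would look the same in the data as one that never occurred, and no later analysis could restore it. At stake are the level of the early AE rates, their consistency between interviewers, and whether they mean the same as the Study Three rates with which they may be pooled.

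**Working it through.** **1. The passages side by side**

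| Element | AE definitions and safety sections | Appendix 6 note and form |
|---|---|---|
| Does relatedness matter for counting? | No | Interviewer is asked to distinguish related from pregnancy-related |
| Who judges causality? | CARM, not study staff by telephone | Study staff, by telephone |
| Comparison with usual state | Needed, since only worsening of an existing condition counts | Prompted, but no field for the answer |
| Symptoms set aside | Not foreseen | No field |

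The conflict lies in the relatedness wording. The prompt about the usual state agrees with the AE definition; its only defect is that the answer is not recorded.

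**2. What else captures these events**

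- Survey 1 asks about contact with a doctor for any reason, limited to 24–48 hours after vaccination.
- The four-week survey (Appendix 7) has an open item on any event in the month, relists muscle aches and severe nausea or vomiting, and asks about seeing a doctor. It has no relatedness prompt.
- Headache, fatigue and fever are not relisted there, so their recovery depends on the open item and on recall at four weeks.

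**3. The plan's own figures**

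Input: n = 300, from Sample size and power for Study Two. The exact (Clopper-Pearson) 95% limits for x events are the 2.5% quantile of Beta(x, n − x + 1) and the 97.5% quantile of Beta(x + 1, n − x).

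- 30/300: 6.85–13.97% (stated 7–14%)
- 15/300: 2.83–8.11% (stated 2.8–8.1%)
- 3/300: 0.21–2.89% (stated 0.2–2.9%)

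The stated intervals reproduce. They reflect sampling error only.

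**4. Possible size of the bias**

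Let p be the true proportion of women with a new or worsened event and f the share of those events dropped. Neither is in the protocol; all values below are assumptions. The expected observed rate is p(1 − f); for example 10% × (1 − 0.25) = 7.5%. Coverage is the binomial probability, with n = 300 and success probability p(1 − f), that the exact interval contains p.

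| True p | f = 10% | f = 25% | f = 50% |
|---|---|---|---|
| 5% | 4.5%, coverage 96% | 3.75%, 88% | 2.5%, 48% |
| 10% | 9.0%, 94% | 7.5%, 74% | 5.0%, 12% |
| 30% | 27%, 80% | 22.5%, 17% | 15%, 0% |

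A small loss hardly matters for uncommon events. A moderate loss matters for common ones.

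If Study Three were free of any such sorting, pooling 300 with 300 at p = 10% would give (10% + 9.0%)/2 = 9.5%, (10% + 7.5%)/2 = 8.75% or (10% + 5.0%)/2 = 7.5%. Whether Study Three was free of it is not shown.

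**The case against.** The strongest reply is that the note is only a loosely worded probe. It stands once, under the injection-site question, where pregnancy is rarely a rival explanation, and it is not repeated at the question on other symptoms. It never tells the interviewer to code a symptom as absent. To tease out can mean to elicit more fully, and the only question it supplies is the baseline comparison that the AE definition requires. The statements on causality sit in the reporting sections and describe formal assessment; they do not address interview technique.

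Much of this stands. The downward direction is an inference that depends on interviewers applying the note to general symptoms, and the baseline prompt should be kept. What does not fall away is the text itself. The note speaks of symptoms and events in general, makes most sense for symptoms that pregnancy can also cause, and asks for a distinction by relatedness that the definition excludes.

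Stronger readings are tempting but not supported:

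- A reader might infer that dismissed events never reach CARM. Under Other adverse event reporting, non-serious events go there only at the discretion of the clinician or investigator, so mild headache or fatigue might not be sent in any case.
- A reader might infer that Study Three was collected without such a note, because the question list in Appendix 8 has none. That list names data items, not interviewer wording. Appendix 8 refers to a standard script and a telephone questionnaire, and neither is shown under its own heading.
- A reader might infer that events are lost altogether. The routes in step 2 of the working give partial capture without a relatedness prompt, above all for medically attended events.

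**Conclusion.** The concern holds as an internal contradiction with a possible, unquantified bias. The note's relatedness wording conflicts with the AE definition and with the statements on causality, and the form records neither the baseline comparison nor symptoms set aside. If the note is applied to the general symptoms, each event it removes lowers the early AE rate, and uneven use makes the rate depend on the interviewer. Events most exposed are mild, unattended early ones such as headache and fatigue.

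The protocol does not show that this loss will occur or how large it would be. The figures in the working rest on assumed true rates of 5–30% and assumed losses of 10–50%. The true rate there means new or worsened events only, so unchanged pregnancy symptoms are not counted as losses. This should be fixed; it does not undermine the design.

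**What to change.** - Delete from the Appendix 6 note the wording that separates vaccination-related from pregnancy-related symptoms.
- Record every symptom since vaccination, with its onset.
- Keep the comparison with the woman's usual state, as a separate coded field: present before vaccination or not and, if present, worse or more frequent or not.
- Count new or worsened events as AEs under the protocol's definition, and leave attribution to CARM.
- Before pooling, confirm that the Study Three interviews used equivalent wording, and report the difference if they did not.

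The cost is one shortened note and one added field in an existing interview. Crude AE rates may come out somewhat higher. The change helps only the interviews that follow it, because symptoms already set aside leave no record.

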
Level one diagnostic certainty is: Any description of morphological or physiological change at or near the injection site that is described or identified by a health care provider
 
Level two diagnostic certainty is: Any description of morphological or physiological change at or near the injection site that is described or identified by another person
 
Categories for event classification
 
Level 1: as specified in the case definition for a local reaction
 
Level 2: as specified in the case definition for local reaction
 
Insufficient evidence for a local reaction Not a case of a local reaction
 
Interval for onset of local reaction or first observation
 
>0-24 h 25-48 h 49-72h 73h – 7 days >7 days
 
Include numbers of subjects with local reactions newly present at each specified time as %.
 
Diameter of the local reaction
 
>0.0 - <1.0 cm ≥1.0 – 2.5 cm
	
Fever
 
Endogenous elevation of at least one measured body temperature of ≥38°C
 
Time intervals
 
0 – 24hr Day 1 0 – 24hr Day 2 Day 3-7...
 
Increments
 
<38°C 38.0-38.4°C 38.5-38.9°C Etc.... >41°C

≥2.5 – 5.0 cm ≥5.0 - <10.0 cm ≥10.0 - <15.0 cm ≥15.0 - <20.0cm ≥20.0 - <30.0 cm ≥30.0 cm
 
Pain scale to include measure of functionality
 
0 = No pain 1 = Mild, still able to move arm normally 2 = Moderate, hurts to move arm normally or to touch 3 = Severe, unable to move arm
	
--	--

Ethical considerations

Ethical approval for this study will be obtained from the NZ Ministry of Health and Disability Ethics Committee. These guidelines are based on statements from NZ and international guidelines, including the World Medical Association Declaration of Helsinki: Ethical principles for medical research involving human subjects (WMA 2008) and the Council for International Organizations of Medical Sciences' International Guidelines for Ethical Review of Epidemiological Studies (CIOMS 1991).

Details about the National Ethics Advisory Committee and the Ethical Guidelines for Observational Studies can be accessed <http://neac.health.govt.nz/streamlined-ethical-guidelines-health-and-disability-research>

Whilst we are not undertaking any clinical work (there is no intervention, only observation), we will be observing the standards required by the national ethics committee and GCP standards, in which our team are familiar.

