¹⁰Tavares et al Pregnancy and safety outcomes in women vaccinated with an AS03-adjuvanted split virion H1N1 (2009) pandemic influenza vaccine during pregnancy: A prospective cohort study. *Vaccine* 2011;29:6358

[figure not shown]

Figure: Percentage of subjects 19–64 years with solicited local and general symptoms during 15 days after vaccination

Fever = oral temperature $\geq 37.5^{\circ}\text{C}$ (99.5°F). Grade 3 referred to redness and swelling of diameter ≥ 50 mm; oral temperature $> 39.0^{\circ}\text{C}$ ($> 102.2^{\circ}\text{F}$); and for all other symptoms, prevented normal activity. From Weston et al, 2009.⁸

Study assessments and procedures

Scheduled assessments	Adverse events in mother	Outcomes for infant	Both mother and baby
At enrolment	
¹First contact with mother by phone (standard script, Appendix 2) as soon as possible after identification to
 
 • Provide information about study and obtain detailed informed consent for participation (written consent form sent out if verbal consent given by phone) • capture any solicited adverse events within first 48 hours and first 7 days of receiving vaccine (s) 
Contact GP once consent obtained to obtain details of vaccination (Appendix 3)
		
Contact with mother monthly either by phone or e-mail⁴. If infant has symptoms* consistent with pertussis or a significant contact** with proven case will be invited for clinical review by study team Paediatrician.
 
If an unsolicited adverse event is noted during these calls, it will follow the same safety reporting procedures as other AEs in the study.

4 weeks since vaccine administration	
²Written questionnaire (Appendix 5) to capture any solicited adverse events in mother up to 4 weeks after receipt of vaccine (s)
		
6-week check	
Written questionnaire (Appendix 6) administered by telephone to GP to
	
Written questionnaire (Appendix 6) administered by telephone to GP practice to
	

Pertussis in Pregnancy Safety (PIPS) Study Protocol
Confidential
Not for Public Circulation or Reproduction

	determine pregnancy outcome and medically attended adverse events in mother since last contact.	capture birth history, weight and head circumference, any congenital abnormalities, neonatal death (<29 days) Details of 6-week check and confirm receipt of 6-week vaccination. Document any prior GP or hospital visits.	

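### Survey 1 does not say whether a reaction's diameter is its largest size or its size at the call, nor when it was measured, so diameters may be understated and may vary with call day

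*Protocol*

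**What the plan says.** Appendix 6 is titled "PIPS Study Patient Participant Phone Interview 1 (48 hours–7days post vaccine"). Its preamble says that the questions "ask about your memory of events for the period immediately (within 48 hours") after the dose, and the lead-in to the local-reaction items then asks about the time since vaccination.

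The sizing instruction is "If you have had any redness or swelling, use the clear plastic measure the practice nurse gave you". It continues: "Use the smallest circle you can use to cover all of the redness or swelling, and this will give you the measurement of the reaction".

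Item 1a reads "Has there been any redness where the injection was given". Items 1b (induration) and 1c (swelling) cover reactions that are present or past. In all three, a positive answer leads to "Yes, take measurement (measure tool used", with *estimate* as the alternative tick, followed by the size bands. Item 1e records onset and duration in bands for each type of local reaction.

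In the main text, the table of definitions for local reactions and fever lists "Diameter of the local reaction" as a set of bands, without defining it as a maximum or fixing a time. The Canterbury protocol (Appendix 8) repeats those bands. The Study Two eligibility form (Appendix 1) has the practice give the woman the measuring strip before she goes home. The Study Two enrolment text says that first contact is made as soon as possible, and a footnote accepts recall for women contacted retrospectively.

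**The concern.** The items ask about a reaction at any time since the dose, while the size follows from an instruction to measure, given in an interview that may fall anywhere from 48 hours to 7 days later. Three kinds of value can enter the same band: a size measured at the peak, a size measured on the day of the call, and a size recalled. The form separates the last from the first two, but not the first two from each other.

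The endpoint of Study Two is the rates and patterns of adverse events, and the diameter bands are the only size grade for redness, induration and swelling. Pain has its own functional scale. If some women are banded on a remaining size, larger reactions may be under-counted, and part of the spread between bands may reflect when each woman was reached.

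**Working it through.** No figure in the plan depends on this point, so there is none to reproduce. The check compares what each part of the Protocol fixes about the diameter.

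| Source | What it fixes | What it leaves open |
|---|---|---|
| Appendix 6, title and preamble | Interview at 48 hours to 7 days; memory of the first 48 hours | Whether the size belongs to the recalled period or to the call |
| Appendix 6, sizing instruction | Tool and method (smallest covering circle, or ruler) | Time of measurement; largest or current |
| Appendix 6, items 1a to 1c | Past or present reaction; tool or estimate; band | Peak or call-day value |
| Appendix 6, item 1e | Onset and duration bands | When the size was taken |
| Definitions table, main text | Band limits | Maximum or not; time point |
| Appendix 1 | Strip handed over at the practice | Any instruction on when to use it |

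**Step 1: can a call-day size be recorded?** Yes. The instruction to measure is part of the interview script and sets no time. A woman whose reaction is still present can follow it by measuring during the call.

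**Step 2: in which direction would such a reading err?** The size at the call cannot exceed the largest size reached up to then. A correct tool reading at the call therefore equals that largest size or falls below it.

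**Step 3: what about the other values?** A size measured at home at the peak carries no such error. A recalled size can err either way. The net direction across all women is therefore not determined, although the call-day readings can only pull downward.

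**Step 4: can the analysis sort this out?** No. The tool tick covers both peak and call-day readings. Onset and duration bands do not date the measurement. Knowing the date of the call would not help either, because it does not show whether the woman measured then or earlier.

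**Step 5: how large is the effect?** It depends on how many women measure at the call and how far their reactions have shrunk. The Protocol gives neither, so no figure is offered.

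For contrast, the serious adverse event form (Appendix 10) explicitly asks for the greatest intensity reached over the whole event. Survey 1 has no equivalent for local reactions.

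**The case against.** The strongest reply is that the form can be read as asking for the size of the reaction the woman had. She has the strip before she leaves the practice, the preamble asks about memory of the first 48 hours, the items use past or present-or-past wording, and an estimate is allowed. All of this stands. A reader might infer that measurement happens only during the call, but the documents do not support that: the form permits a call-day reading without requiring one.

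A reader might also infer that diameters are in fact understated. That goes too far. It would need a time course for reaction size and a known mix of readings, and neither is given.

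The full participant information sheet (Appendix 5) is handed over with the strip and is not in the text available. It may already tell the woman when to measure, so no gap can be asserted there. Even so, Survey 1 would not show which women had followed it.

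Two further consequences are tempting. One is that practices would appear to differ because of call delay, but no comparison of reactions between practices is planned. The other is that the share at 5 cm or more would look falsely low beside the published figure in Appendix 8, "Percentage of subjects 19–64 years with solicited local and general symptoms during 15 days after vaccination", whose legend counts redness and swelling of at least 50 mm as grade 3. That figure is background in the Canterbury protocol. Study Two defines no endpoint at 5 cm and plans only to discuss its rates in the context of earlier ones.

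Finally, size is not the only information on a local reaction: duration is recorded, and a later item covers contact with a doctor. Neither replaces a defined diameter.

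**Conclusion.** The point holds as an ambiguity in the form. Items 1a to 1c and the definitions table leave open whether the diameter is the largest size or the size at the call, and nothing records when it was measured. Diameters may therefore be understated and may vary with call day. This rests on the wording of the form and on the fact that a current size cannot exceed the largest size so far. It assumes that at least some women with a continuing reaction measure at the call. The size of the effect cannot be estimated from the documents.

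The matter is minor. It contradicts no stated figure and leaves the rates of any redness, induration or swelling untouched. It is worth correcting because the missing information cannot be recovered once the interviews are done.

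**What to change.** - Reword items 1a to 1c to ask for the largest size since the injection.
- Replace the present two-way tick with three options: *measured at largest*, *measured at call*, *estimated*.
- Define the diameter in the main-text table as the largest size, and report the bands on that basis, with call-day and estimated values shown separately.
- If the information sheet given with the strip does not already say so, add one sentence asking the woman to measure when the reaction is at its largest.

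The cost is a few words, one revised tick-box and possibly one sentence, with no extra contact. The downside is that some largest sizes will be recalled instead of measured, which the new tick-box makes visible. The value will also cover only the period up to the call. Because the Protocol foresees joint analysis of maternal outcomes with Study Three, check whether the Canterbury survey sizes reactions in the same way before diameter bands are pooled.
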